13.4.5 Analyses of Exploratory Endpoints

We will correlate pre and/or post-transplant serum reactivity to each autoantigen and to donor HLA with our primary endpoint to prospectively and independently test the hypothesis that autoantibodies can be used as predictors of incipient injury. We will also correlate the presence of serum antibodies with positive C4d staining of the graft tissue (to be collected as part of the clinical component of the study).

To test the hypothesis that rituximab prevents induction of de novo autoantibodies and or DSA, we will compare titers of autoantibodies (or DSA) between the rituximab and control groups. Development of antibodies to either DSA or self-antigens or both and the kinetics of antibody development (time course following transplantation) will be correlated with clinical evidence of AMR and BOS as determined in the

clinical part of study described above and the ISHLT criterion. While the absolute numbers of patients in each group with preexisting autoantibodies or DSA is anticipated to be small (thus limiting power) we will compare and report pre vs post-transplant titers in each case to determine if rituximab impacts preexisting antibody.

The results will be analyzed for development of PGD, development of DSA, diagnosis of AMR and BOS. In addition we will also determine any correlation which may exist between the strength of antibodies detected for DSA, HLA and each antibody to self-antigens either alone or cumulatively and clinical outcomes such as PGD, AMR and BOS.

We will analyze DSA and each type of antibody separately. The DSA and autoantibody data will consist of binary (positive/negative) or ordinal (negative/weak positive/strong positive) responses measured repeatedly at scheduled and unequally-spaced intervals. With these features of the data and at this sample size, it may not be feasible to obtain estimates of treatment effect at each time-point using a single statistical model with rituximab and time main effects and their interaction as covariates. Therefore we will describe the treatment effect over the course of the follow-up period.

The hazard ratio for the association between development of antibodies and clinical outcomes (the endpoint and its components, and the secondary incidence endpoints) will be estimated with its 90% confidence interval using a Cox proportional hazard model with presence or absence of antibodies as time-dependent repeated measures covariates, stratified by treatment group. We will model the association of each antibody on each outcome separately and in combination.

We will also estimate odds ratios with 90% confidence intervals for the associations between each of the various serum antibodies and C4d staining of the graft tissue. We will estimate these odds ratios at each time point between each pair of antibodies and each antibody and C4d result, both cross-sectional, and cumulative, in which case we would treat any subject with a current or prior positive result as positive for that particular antibody.

13.4.6 Descriptive Analyses

Selected subject baseline clinical and demographic characteristics, as well as use of concomitant medications and study subject disposition will be summarized using standard descriptive statistics for continuous and categorical variables.

13.5 Interim Analyses

No interim analyses are planned. However, as described in section 12.8.2., the DAIT Transplant DSMB will periodically review safety data in open and/or closed sessions.

13.6 Sample Size Considerations

Planning this study indicates a sample-size analysis that is congruent with our focus on estimates and confidence intervals. Accordingly, simulated study data using a Weibull distribution with parameters chosen to match our expectation that the outcome rate in the control group will be 74% at one year and 53% at two years, with hazard ratios of 0.40 and 0.33. For the purposes of the study only large group differences are clinically relevant, and therefore this effect size is reasonable.

Sample-sizes between N = 25 + 25 and N = 30+ 30 are feasible, as argued elsewhere. We also looked at N = 35 + 35, but acknowledge this probably not obtainable.

5000 individual trials were run for each combination of total sample size (N = 50, 60, 70) and true hazard ratio (0.40, 0.33). Each trial's dataset was analyzed using a standard Cox proportional hazards model and the estimated log (HR) and its standard error were obtained. Using the criteria given in **Table 21**, each trial's estimate and upper confidence limit was rated as being "excellent," "good," "fair," or "lacking" in supporting the rituximab efficacy. The obtained proportions are given in **Table 22**.

Table 21: Criteria for Estimating Upper Confidence Limit

Evidence for Efficacy	Estimated Hazard Ratio	Upper 90% Confidence Limit
"Excellent"	<0.55	<0.85
"Good"	<0.60	0.85 – 1.10
"Fair"	<0.70	1.10 – 1.20
"Lacking"	Any	>1.20

Table 22: Upper 90% Confidence Limits by HR and Sample Size

Sample Sizes	25+25		30+30		35+35	
	0.04	0.33	0.04	0.33	0.04	0.33
True Hazard Ratio						
Evidence for Efficacy						
"Excellent"	0.39	0.50	0.46	0.59	0.51	0.64
"Good"	0.22	0.21	0.23	0.21	0.24	0.20
"Fair"	0.07	0.06	0.06	0.05	0.06	0.04
"Lacking"	0.33	0.24	0.25	0.16	0.19	0.12

In addition, although the primary analysis is based on a Cox regression model, a simple power and sample size assessment using the less efficient log-rank test indicates that 25 subjects in each group will provide greater than 80% power to detect a HR of 0.45 for the treatment effect using a one-sided test at the 0.05 level of significance.

14. Identification and Access to Source Data

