Secondary Clinical Endpoints	
Post-transplant outcomes including:
 
 1. Incidence of chronic allograft dysfunction, listing for retransplantation and death during the follow-up period, which will be a minimum of 12 months post-transplant; 2. Incidence of Primary Graft Dysfunction; 3. Incidence of Grade A Acute Rejection during the follow-up period, which will be a minimum of 12 months post-transplant; 4. Incidence of Antibody Mediated Rejection during the follow-up period, which will be a minimum of 12 months post-transplant; 5. Incidence of tacrolimus variability threshold during the follow-up period, which will be a minimum of 12 months post-transplant; 6. Percentage of participants meeting tacrolimus variability threshold who complete tacrolimus variability intervention; 7. Magnitude of change in standard deviation of tacrolimus levels following intervention. 
Post-transplant safety outcomes including:
 
 1. Incidence and severity of infection episodes;

	2. Serious adverse events related to rituximab.
Secondary Mechanistic Endpoints	
 1. Incidence and kinetics of DSA and autoantibodies, specifically Collagen V (CoIV) and k-alpha-1 tubulin ($\kappa\alpha 1T$); 2. Frequency, kinetics, phenotype and function of peripheral B cells; 3. Frequency, kinetics and cytokine profiles of allo- and auto reactive T cells; 4. Incidence and quantity of B cells and B cell proximity to other cells in the graft tissue.
Accrual Objective	50 randomized pediatric lung transplant recipients
Study Duration	
4.5 years (3.5 year accrual + 1-4.5 year follow-up period)
 
All participants will be followed for a minimum of 1 year post-transplant. Participants will continue follow up visits (up to 4.5 years post-transplant) until the last participant completes 1 year of follow-up.

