13.4 Analysis Plan

The overall focus of our statistical analysis of the clinical portion of the study will be on the estimation of hazard ratios (HR) and risk ratios (RR) and their two-sided 90% confidence intervals comparing the rituximab and placebo groups on each endpoint of the study. Focusing on estimates and confidence intervals will allow us to assess the range potential efficacies as best we can within the limitations imposed by studying such a rare pediatric population.

Further detail describing the analysis plan will be contained in a Statistical Analysis Plan (SAP) that will be maintained by the SACCC and updated as necessary.

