13.4.2 Primary Analysis of Primary Endpoints /Outcomes

We will use competing-risks Cox proportional hazards models to compare treatment groups on the time to endpoint, right-censored at the end of the two-year follow-up period or at time of loss to follow-up. This model, as opposed to a time-to-first-event model, will allow us to estimate a separate hazard function for each type of outcome as well as the overall outcome, and thus assess whether the effect of rituximab is the same for all outcome types¹⁰⁰. Our focus will be on the estimates of these hazard ratios (HR) and their two-sided 90% confidence intervals, with $HR < 1$ indicating rituximab efficacy. We will assess whether HR is constant throughout follow-up, or if the effect of rituximab is confined to early or late portions of the study periods through the use of time-dependent covariates. Model diagnostics will include assessment of the proportional hazards assumption and of each observation for influence on model parameters. The model will be run on both the ITT and PP populations, as events allow.

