7.2.2. Primary Analysis of the Primary Endpoint

As the data allow, a Cox proportional hazards model will be used to compare treatment groups on the time to endpoint, allowing for right-censoring at the end of the follow-up period or at time of loss to follow-up. Estimates of the hazard ratios (HR) and their two-sided 90% confidence intervals will be produced. HR estimates <1 will indicate rituximab efficacy. For example, if an HR<0.85 is considered as indicating clear efficacy, then an HR estimate and 90% confidence interval of 0.33 (0.16, 0.68) will provide excellent support for clear efficacy; whereas an HR= 0.55 (0.28, 1.07) would provide fair to good support for efficacy, even though it would fail to reach significance for the usual test of HR= 1.

The model will be run on both the ITT and PP samples, as events allow.

Model diagnostics will include an evaluation of the proportional hazards assumption and of each observation for influence on model parameters. The proportional hazards assumption will be assessed by testing for a significant interaction between treatment group and the time-to-event variable.

An example of SAS code to be used for the primary model:

```
Proc phreg;  
  class treatment_group(ref='Placebo');  
  model event_day * endpoint_status(0) = treatment_group intterm /  
risklimits ties=efron alpha=0.1;  
  intterm= treatment_group_01 * event_day;  
run;
```

Note: *intterm* represents the interaction term that can be used to test the proportional hazards assumption and *treatment_group_01* represents *treatment_group* coded as a 0, 1 variable where 0=placebo and 1=rituximab. This term will be used for testing the assumption only and will not be included in the final model.

To estimate the hazard function of each of the components, separately, the following models will be used.

An example of SAS code to be used for the analysis of competing risks:

*This is the model for Death;

```
Proc phreg;  
  class treatment_group(ref='Placebo');  
  model event_day * endpoint_status(0,1,2) = treatment_group /  
risklimits ties=efron alpha=0.1;  
run;
```

*This is the model for Listed for Re-transplant;

```
Proc phreg;  
  class treatment_group(ref='Placebo');  
  model event_day * endpoint_status(0,1,3) = treatment_group /  
risklimits ties=efron alpha=0.1;  
run;
```

*This is the model for Chronic Allograft Dysfunction;

```
Proc phreg;  
  class treatment_group(ref='Placebo');  

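### The power above 80% claimed for a hazard ratio of 0.45 with 25 per group does not follow from the protocol's own assumptions; it is about 50% to 60%, and Table 22 contradicts the claim

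*Protocol*

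**What the plan says.** Protocol 13.6 bases the sample size on simulation. Weibull data are generated so that the "outcome rate in the control group will be 74% at one year and 53% at two years", with true hazard ratios of 0.40 and 0.33. Each simulated trial is graded *excellent*, *good*, *fair* or *lacking* from its estimated hazard ratio and upper 90% limit (Table 21). The proportions appear in Table 22, "Upper 90% Confidence Limits by HR and Sample Size". For 25+25 they are 0.39 / 0.22 / 0.07 / 0.33 at HR 0.40 (the column header prints 0.04) and 0.50 / 0.21 / 0.06 / 0.24 at HR 0.33.

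A closing sentence then makes a conventional power claim: "25 subjects in each group will provide greater than 80% power to detect a HR of 0.45 for the treatment effect". The test named there is the log-rank, one-sided at 0.05.

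The section gives no event count, follow-up horizon, accrual pattern or dropout rate for either calculation. Other sections bear on the horizon:

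- Protocol 13.4.2 has the primary analysis "right-censored at the end of the two-year follow-up period or at time of loss to follow-up".
- SAP 7.2.2 has no two-year cut, "allowing for right-censoring at the end of the follow-up period or at time of loss to follow-up".
- The synopsis (Study Duration) says "All participants will be followed for a minimum of 1 year post-transplant", with 3.5 years of accrual and follow-up of up to 4.5 years.

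The SAP has no sample-size section.

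**The concern.** Log-rank power depends on the number of events, and 50 children with roughly half of the controls event-free at two years will not produce many. A claim of more than 80% at HR 0.45 also sits oddly beneath a table in which a third of trials at the more favourable HR 0.40 are graded *lacking*.

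This is the only conventional power figure in either document. A monitoring board, ethics committee or later reader could take a null result to come from a trial with a better than four-in-five chance of detecting HR 0.45, when the chance was nearer one in two.

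**Working it through.** **1. Events needed for the stated power.** With 1:1 allocation, one-sided 0.05 and HR 0.45 (Schoenfeld):

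d = 4 × (1.645 + 0.842)² / (ln 0.45)² = 4 × 6.185 / 0.638 ≈ 38.8 events out of 50 subjects.

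**2. Control-arm curve.** A cumulative event rate cannot fall from 74% to 53%, so these are event-free proportions (26% and 47% with events). A Weibull cumulative hazard λt^k through both points has λ = −ln 0.74 = 0.301 and k = log₂(0.635 / 0.301) = 1.076, where 0.635 = −ln 0.53. The rituximab arm has 0.45 times this hazard.

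**3. Expected events and power at 25+25, HR 0.45, no dropout.** Where follow-up varies it is assumed uniform on 1 to 4.5 years. Power = Φ(|ln 0.45| × √(d/4) − 1.645).

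| Follow-up | Events, control + rituximab | Schoenfeld power | Simulated log-rank power |
|---|---|---|---|
| 1–4.5 y, cut at 2 y (protocol 13.4.2) | 11.04 + 5.78 = 16.8 | 50% | 49% |
| 2 y for all 50 | 11.75 + 6.21 = 18.0 | 52% | 51% |
| Full 1–4.5 y (SAP 7.2.2) | 14.19 + 8.11 = 22.3 | 60% | 58% |
| 4.5 y for all 50 (not the design) | 19.53 + 12.38 = 31.9 | 73% | 72% |

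For the first row: 0.7985 × √(16.8/4) − 1.645 ≈ −0.01, and Φ(−0.01) ≈ 0.50. With an assumed dropout of 5–10% per year, simulated power falls to 45–47% under the two-year cut and 53–55% with full follow-up.

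**4. Table 22 alone.** One-sided 0.05 significance corresponds to an upper 90% limit below 1.00. At 25+25 and HR 0.40:

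- *Lacking* (limit above 1.20) is 0.33, so power is at most 1 − 0.33 = 0.67.
- *Excellent* plus *good* (limit below 1.10) is 0.39 + 0.22 = 0.61, and requiring a limit below 1.00 is stricter.
- HR 0.45 is a weaker effect, so its power is lower again. Even the HR 0.33 column allows at most 1 − 0.24 = 0.76.

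**5. Can Table 22 be reproduced?** Yes. Simulation with the curve in step 2, uniform 1–4.5 year follow-up and a two-year cut (20,000 trials per cell) matches all 24 printed cells to within 0.017. For 25+25 at HR 0.40 it gives 0.40 / 0.21 / 0.07 / 0.32. Two years for everyone misses by up to 0.050, and full follow-up by up to 0.140. This supports the event-free reading and indicates, though section 13.6 does not say so, that the table rests on a two-year cut. Under that design the chance of an upper limit below 1.00 is 0.54 at HR 0.40 and 0.46 at HR 0.45.

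**6. Readings that might rescue the sentence.**

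- 74% as a one-year event rate, constant hazard, two years' follow-up: 40.9 events, 82%. This contradicts 53% at two years.
- Rates reversed (53% then 74% with events), all 50 followed for 4.5 years: 40.7 events, 82%. This contradicts both the printed order and the follow-up design.
- Rates reversed, two years' follow-up: 29.9 events, 70%.
- Every subject having an event: 88%.

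No reading that respects both the printed rates and the design reaches 80%.

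**The case against.** The strongest reply is that the sentence carries little weight. Section 13.4 puts the emphasis on estimation: "Focusing on estimates and confidence intervals will allow us to assess the range potential efficacies as best we can". The sample size is argued from feasibility and Table 22, the log-rank figure is offered as a simple addition, and Table 22 already discloses a 24–33% chance of *lacking* evidence at 25+25. This stands and limits the consequence, but it does not make the figure right.

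Second, section 13.6 gives no horizon for the sentence, so the 50% and 60% need inputs from elsewhere plus an assumption of even accrual. That is fair. The 60% is also the softer number: it extrapolates the curve beyond two years, and simulation gives 58%. The Table 22 contradiction has no such dependence if the table and the sentence share a horizon. If they do not, even 4.5 years for every subject gives only 73%.

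Third, an upper Cox limit below 1.00 is a Wald criterion, whereas the sentence concerns the log-rank test. The two differ by only two or three percentage points here.

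Finally, the fault may lie in mislabelled rates rather than in the arithmetic. That could explain how the figure arose; it does not validate it.

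**Conclusion.** The power statement is wrong as written. Under the section's control rates read as event-free, even accrual and no dropout, power at HR 0.45 with 25 per group is about 50% with two-year censoring and about 60% with all follow-up used. The claim is therefore about 20 to 30 percentage points too high, and dropout would widen the gap. Expected events are 17 to 22 against the 39 required. The conflict with Table 22 needs no assumed accrual or dropout. The consequence is a misleading stated power that should be corrected; the analysis, sample size and decision rule are unaffected.

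**What to change.** In protocol 13.6, take one of two courses.

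1. Delete the power sentence and rely on Table 22. This is the cleaner course, because it needs no new assumption.
2. Restate it: with 25 per group, control event-free rates of 74% at one year and 53% at two years, even accrual and no dropout, a one-sided 0.05 log-rank test has about 50% power for HR 0.45 when 1–4.5 year follow-up is censored at two years, or about 60% when all of that follow-up is used.

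In either case, label 74% and 53% as event-free rates, correct the Table 22 header from 0.04 to 0.40, and state the follow-up horizon, accrual pattern and dropout behind every figure kept. The two-year figure is the one that appears to share Table 22's basis. If full follow-up is chosen, rerun Table 22 on that horizon as well. Do not quote a hazard ratio at which 80% power is reached unless it is simulated under the same horizon as the table.

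The cost is a text correction, or a short simulation rerun if full follow-up is adopted. It needs no additional patients and no change to the analysis.

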14.1. Source Data

Source documents and source data are considered to be the original documentation where subject information, visits consultations, examinations and other information are recorded. Documentation of source data is necessary for the reconstruction, evaluation and validation of clinical findings, observations and other activities during a clinical trial.

14.2. Access to Source Data

The site investigators and site staff will make all source data available to the DAIT/NIAID, as well as to relevant health authorities. Authorized representatives as noted above are bound to maintain the strict confidentiality of medical and research information that may be linked to identified individuals.

15. Protocol Deviations

15.1. Protocol Deviation Definitions

Protocol Deviation – The investigators and site staff will conduct the study in accordance to the protocol; no deviations from the protocol are permitted. Any change, divergence, or departure from the study design or procedures constitutes a protocol deviation. As a result of any deviation, corrective actions will be developed by the site and implemented promptly.

Major Protocol Deviation (Protocol Violation) - A Protocol Violation is a deviation from the IRB approved protocol that may affect the subject's rights, safety, or well-being and/or the completeness, accuracy and reliability of the study data. In addition, protocol violations include willful or knowing breaches of human subject protection regulations, or policies, any action that is inconsistent with the NIH Human Research Protection Program's research, medical, and ethical principles, and a serious or continuing noncompliance with federal, state, local or institutional human subject protection regulations, policies, or procedures.

Non-Major Protocol Deviation - A non-major protocol deviation is any change, divergence, or departure from the study design or procedures of a research protocol that does not have a major impact on the subject's rights, safety or well-being, or the completeness, accuracy and reliability of the study data.

15.2. Reporting and Managing Protocol Deviations

The study site principal investigator has the responsibility to identify, document and report protocol deviations. However, protocol deviations may also be identified during site monitoring visits or during other forms of study conduct review.

Deviations that impact the ability to assess study outcomes will be collected for this study. Upon determination that a protocol deviation has occurred, the study staff will notify the SACCC by completing a Protocol Deviation eCRF. NIAID, the study PI and DSMB will review deviations on a regular basis. The site will be responsible for reporting deviations to the local IRB according to site-specific guidelines.

16. Ethical Considerations and Compliance with Good Clinical Practice

16.1. Statement of Compliance

This clinical study will be conducted using good clinical practice (GCP), as delineated in *Guidance for Industry: E6 Good Clinical Practice Consolidated Guidance*, and according to the criteria specified in this study protocol. Before study initiation, the protocol and the informed consent documents will be reviewed and approved by the IRB. Any amendments to the protocol or to the consent materials will also be approved by the IRB before they are implemented.

16.2. Informed Consent Process

The consent process will provide information about the study to a prospective participant and will allow adequate time for review and discussion prior to his/her decision. The principal investigator or designee listed on the FDA 1572 will review the consent and answer questions. The prospective participant will be told that being in the trial is voluntary and that he or she may withdraw from the study at any time, for any reason. All participants (or their legally acceptable representative) will read, sign, and date a consent form before undergoing any study procedures. Consent materials will be presented in participants' primary language. A copy of the signed consent form will be given to the participant.

The consent process will be ongoing. The consent form will be revised when important new safety information is available, the protocol is amended, and/or new information becomes available that may affect participation in the study.

